#### 3.10.4 Individual service user outcome data

##### LLBD Weight Management Programme

For the individual level outcome data, the analysis will be descriptive, displaying mean weight loss, mean short form Warwick Edinburgh score, and mean scores for the Health Literacy Questionnaire domains at the three time points. Then multiple regression will be used to test differences in changes in means between baseline and 12 weeks in the trained and untrained groups. We will also consider whether people who had an improvement in the Health Literacy Questionnaire domains were more likely to have better outcomes.

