#### **3.2 Timing of intervention**

For both programmes staff will receive Verbal Health Literacy training and implementation support from the Health Literacy Officer. Outcomes will be measured for service users joining a programme run by trained staff. Where appropriate and for comparison, outcomes will be measured for service users joining a programme run by non-trained staff during the same period.

Half of the staff from the weight management programme (4/8) will receive the training to allow for controlled before and after comparison of outcomes. One member of staff takes a group of service users through their weight management sessions so it will be possible to identify service users linked to trained and untrained staff. This is not possible for the pulmonary rehabilitation service where different staff work with different service users throughout the programme. All six physiotherapists and two specialist nurses from the pulmonary rehabilitation service will receive the training. The focus is on physiotherapists and specialist nurses because they spend most time with service users.

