### **3.5. Assessment of individual service user health and wellbeing outcomes**

The two services collect a range of data about service user outcomes. For the weight management programme service users complete routine service assessments at baseline12 and 26 weeks. For the pulmonary rehabilitation programme assessments are carried out at baseline and on completion of the programme at six weeks. That is after attendance at 8-12 sessions. This is so change can be measured over time.

The researcher will seek consent to access this data for all those service users who attend either of the two participating programmes during the intervention period.

This data will be available at individual service user level if service users give informed consent. This data is stored on the services databases. Only anonymised data will be shared with the researcher.

Additional anonymised demographic data of attendees, that is routinely collected by the services, will be shared with the researcher. This data will include gender, ethnicity, age and index of multiple deprivation.

Primary and secondary outcomes for each of the two participating services will be collected. The outcomes are:

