### **3.7. Assessment of changes in outcomes (at a service level)**

Aggregate programme level data will be obtained from the two services for a three - six month period in 2024 when trained staff have delivered programmes and a corresponding three- six month period in 2023. This will allow comparable measurement of change over time at a service level.

For the weight management service, a control group will consist of programmes run by non-trained staff. The same aggregated data will be obtained for this control group. Individual level patient data will not be shared with researchers because not all service users will have consented to this.

The aggregate data will include:

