### **3.8 Recruitment**

We will recruit staff delivering Verbal Health Literacy training during a three month period in 2024.

IRAS 336469

V2.0 13052024

We will recruit service users from two services, one within Derbyshire Community Health Services NHS Trust and one within the Local Authority. Service user recruitment is likely to take place over a six month period to recruit the minimum required sample. This is because both services run on a rolling basis. That is week 1 for one person could be week 6 for another.

We will recruit service users who enrol on the 12 week weight management programme and 6 week pulmonary rehabilitation programme after staff have (or have not) attended the Verbal Health Literacy training.

That is:

- Public Health Intervention Advisors and service users from the Live Life Better Derbyshire tier two weight management service.
- Physiotherapists, specialist nurses and service users from the Derbyshire Community Health Services (DCHS) pulmonary rehabilitation service.

Recruitment will commence once HRA and NHS ethics approval is obtained. Written informed consent will be gained for all participants in the study.

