### 3.9.2. Service users' individual outcomes

#### LLBD Weight Management Programme

Between 15-25 people attend each 12 week rolling LLBD weight management programme. 33 programmes are likely to be ongoing between the three month study period in 2024, with a minimum and maximum of 495 and 825 service users joining in total. All service users starting the programmes during the period of the study will be invited to take part when they sign up. We estimate there will be approximately 660 attendees to the LLBD weight management programme. With a response rate of 50% to our request to participate in the evaluation, we expect there to be weight, health and wellbeing and Health Literacy scores at three time points for approximately 330 service users. Approximately 160 service users will be in groups led by trained and 160 in groups led by untrained staff. We expect to see a reduction in weight, an improvement in clinical outcomes and an improvement in wellbeing between baseline and 12 weeks and baseline and 26 weeks for both groups. We expect the changes to be larger in the trained group versus the untrained group. We expect there to be an improvement in Health Literacy domain scores between baseline and 12 weeks (the end of the program) for the trained group and no change for the untrained group.

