#### LLBD Weight Management Programme sample size calculation

From January to March 2023 the mean starting weight was 103.68kg. The mean weight on completion of the 12 week course was 99.60kg. So, the mean weight loss was 4.08 kg for this cohort. This was larger than the mean weight loss of 2.3 kg for behavioural weight management interventions in primary care at 12 months compared with controls (Madigan *et al*, 2022). But people can gain weight after initial loss so we are happy to use the historical Derbyshire data to help calculate a required sample size.

We expect the mean weight loss for the Derbyshire service to be larger in 2024 than in early 2023 potentially due to the health literacy training but also likely to be related to improvements management have made to the service between 2023 and 2024.

We would expect a minimum of a 10% increase in the mean weight loss in the trained group vs. untrained group at 12 weeks, that is, 4.7kg vs. 4.3kg. With an estimated pooled standard deviation of 1.6, a sample size of 252 would be required in each group to detect this size of difference with 80% power at a 5% level of significance. As stated earlier there will be approximately 330 service users in each group who can be invited to take part. We therefore should be able to recruit sufficient numbers (252) to ensure we will be able to detect an improvement in weight loss over time at a service level.

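### The weight analysis and the sample size of 252 per group ignore clustering by advisor (four trained, four untrained), so standard errors are too small and the stated 80% power is not delivered

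*Combined protocol and SAP*

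**What the plan says.** Section 3.2 sets the allocation: "Half of the staff from the weight management programme (4/8) will receive the training to allow for controlled before and after comparison of outcomes". It adds that "One member of staff takes a group of service users through their weight management sessions", so a service user's trained or untrained status is fixed by the advisor.

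Section 3.10.4 gives the individual-level analysis of weight, the primary outcome: "Then multiple regression will be used to test differences in changes in means between baseline and 12 weeks in the trained and untrained groups". No covariates, random effect, robust variance or advisor-level summary is named. Section 3.9.2 gives the expected numbers: "Approximately 160 service users will be in groups led by trained and 160 in groups led by untrained staff". Section 3.8 recruits service users who enrol "after staff have (or have not) attended the Verbal Health Literacy training", so there is no individual-level cohort from before the training. On the demographic data to be shared, Section 3.5 says: "This data will include gender, ethnicity, age and index of multiple deprivation". Neither it nor any other section promises the researcher an advisor or programme code.

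Section 3.9.3, under service-level outcomes, expects a weight loss of 4.7 kg against 4.3 kg and states: "With an estimated pooled standard deviation of 1.6, a sample size of 252 would be required in each group", for 80% power at the 5% level. It counts about 330 users per group as available.

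For the 2023 to 2024 comparison, Section 3.7 says: "Aggregate programme level data will be obtained from the two services". Sections 3.7 and 3.10.5 do not say whether means and standard deviations come by advisor, by programme or pooled by arm.

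The available text mentions neither clustering nor an ICC.

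**The concern.** The advisor is the unit of allocation, and there are only four per arm. Users of the same advisor share that advisor's style, venues and catchment, so their weight changes are likely to be correlated. The theory of change in Section 1.3.7 itself assumes that how an advisor communicates affects weight loss, which makes a zero advisor effect hard to defend. A regression that treats users as independent can therefore report a chance difference between two sets of four advisors as a training effect, with a confidence interval that is too narrow.

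Adjusting for a user's own baseline weight does not help, because it cannot remove a lasting difference between advisors in the weight their users lose. The 2023 to 2024 aggregate comparison is better placed. It can cancel stable advisor differences, though not variation in an advisor's results from one period to the next.

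This regression is the only individual-level test of trained against untrained on the primary outcome, and Section 8 says the findings will inform funding decisions.

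**Working it through.** **Inputs from the documents.** Difference 0.4 kg (4.7 minus 4.3), SD 1.6 kg, 80% power, 5% significance, 252 and about 330 per group (Section 3.9.3); four advisors per arm (Section 3.2); about 160 per group in the individual data (Section 3.9.2), that is 160/4 = 40 per advisor; 33 programmes (Section 1.3.6). **Assumption:** advisor ICC 0.005 to 0.05, with equal numbers per advisor.

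**1. The plan's own figure.** For independent users and a two-sided test:
n per group = 2 × (1.960 + 0.842)² × (1.6/0.4)² = 251.2, rounded up to 252, with power 80.1%. The figure reproduces with a design effect of exactly 1 and almost no slack.

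**2. The regression at 40 users per advisor.** Design effect DE = 1 + (m − 1) × ICC with m = 40. The true standard error is about √DE times the reported one. Type I error of the unadjusted test = 2 × [1 − Φ(1.96/√DE)].

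| ICC | DE | √DE | Type I error | Simulated (20,000 runs) |
|---|---|---|---|---|
| 0 | 1.000 | 1.000 | 5.0% | 4.9% |
| 0.005 | 1.195 | 1.093 | 7.3% | 7.1% |
| 0.01 | 1.390 | 1.179 | 9.6% | 9.2% |
| 0.02 | 1.780 | 1.334 | 14.2% | 13.8% |
| 0.05 | 2.950 | 1.718 | 25.4% | 25.8% |

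In the same simulation a t-test on the eight advisor means held 4.8% to 5.2%.

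Milder case: if users cluster only by programme, with about 330/33 = 10 responders each, ICC 0.01 to 0.05 gives DE 1.09 to 1.45 and type I error 6.1% to 10.4%.

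**3. Power for 0.4 kg.** SE = 1.6 × √(2 × DE/n), with m = n/4. Power comes from the noncentral t on 8 − 2 = 6 df with noncentrality 0.4/SE. The normal approximation is in brackets. Example: n = 160, ICC 0.01 gives SE = 1.6 × √(2 × 1.39/160) = 0.211, noncentrality 1.90, power 36%.

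| ICC | 252 per group | 160 per group | 330 per group |
|---|---|---|---|
| 0 | 65% (80%) | 47% (61%) | 76% (89%) |
| 0.005 | 54% (69%) | 41% (53%) | 62% (77%) |
| 0.01 | 46% (60%) | 36% (47%) | 52% (66%) |
| 0.02 | 35% (47%) | 29% (39%) | 38% (51%) |
| 0.05 | 22% (28%) | 20% (25%) | 23% (30%) |

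**4. Detectable difference at 160 per group.** On 6 df, 80% power needs noncentrality 3.367, so the difference is 3.367 × SE: 0.60 kg at ICC 0, 0.71 kg at 0.01 and 1.03 kg at 0.05.

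**5. Ceiling set by four advisors per arm.** As users per advisor grow, the variance of the difference tends to 2 × 1.6² × ICC/4 = 1.28 × ICC. Setting 0.4/√(1.28 × ICC) to 2.80 gives ICC 0.016 (normal critical value); setting it to 3.367 gives 0.011 (6 df). Above these values no number of users gives 80% power for 0.4 kg.

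**The case against.** - **Different datasets.** The 252 sits under service-level outcomes, while the regression uses consenting individuals, about 160 per group. That is true, and the two are computed separately above. Neither allows for clustering.
- **More users may contribute.** With 330 per group, the normal approximation keeps power at or above 80% up to an ICC of about 0.0038. But the stated 80% is tied to 252, and a 6-df test at 330 has 76% power even at ICC 0.
- **Not all the lost power comes from clustering.** This stands. At 160 per group, power is already 61% with independent users, because 160 is fewer than 252. The fall to 47% at ICC 0 comes from having only 6 df. Only the further fall, to 36% at ICC 0.01 for example, comes from correlation.
- **The ICC is assumed.** This also stands. At ICC 0.001, type I error at 40 per advisor is only about 5.5%. The direction is certain for any positive ICC; the size is not.
- **Silence is not exclusion.** Section 3.2 foresees linking users to trained and untrained staff, and the Section 3.5 list concerns demographics. So an advisor code is feasible, but none is specified, and the regression as written does not use one.
- **The remedy has limits.** Section 3.2 does not say how the four advisors are chosen. No random effect or advisor-level test removes bias from non-random selection.

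**Conclusion.** The concern holds. Followed as written, the Section 3.10.4 regression gives standard errors that are too small for any positive advisor ICC. For an assumed ICC of 0.005 to 0.05 and 40 users per advisor, the true standard error is 9% to 72% larger than reported. The 80% power in Section 3.9.3 holds at 252 per group only if the ICC is 0 and users are tested as independent individuals. These sizes rest on the assumed ICC, equal numbers per advisor and advisors exchangeable between arms; only the first of these is needed to be positive for the direction. This must be fixed before the services extract and anonymise the data, because a missing advisor code may not be recoverable afterwards.

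**What to change.** 1. **Sections 3.5 and 3.10.4.** Include a coded advisor identifier in the anonymised individual data. Name one primary analysis in advance: either 12-week weight on baseline weight and trained/untrained status, with a random intercept for advisor and Kenward-Roger or Satterthwaite degrees of freedom, or a 6-df t-test on the eight advisor-level mean changes. The power figures above apply to the t-test. Advisor as a fixed effect is not an option, because training status is wholly determined by advisor.
2. **Sections 3.7 and 3.10.5.** State that n, mean change and SD are supplied by advisor, or by programme labelled with a coded advisor, for both 2023 and 2024. Compare the advisor-level differences, 2024 minus 2023, between trained and untrained. This requires the same advisors to have worked in both periods, which should be confirmed.
3. **Section 3.9.3.** Restate the power for four advisors per arm over a stated ICC range, without enrolling more.

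**Cost.** Analysis wording, one coded identifier and a stated level of summary; no extra participants. With only eight advisors the results could identify staff, so the data-sharing agreements under Section 5 should cover the code. The downsides are wider confidence intervals, a stated power of about 20% to 47% at 160 per group, and conclusions on weight that may have to be presented as exploratory.

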##### DCHS Pulmonary Rehabilitation Programme

For the individual level outcome data, the analysis will be descriptive, displaying mean CRDQ score, incremental shuttle walking test, LINK, GAD, PHQ-9 and strength test scores. Then multiple regression will be used to test for changes in means between baseline and six weeks. We will also consider whether people who had an improvement in the Health Literacy Questionnaire domains were more likely to have better CRDQ scores.

#### 3.10.5 Aggregate service data

For the aggregated outcome data we will compare mean change in an outcome in a three month period before the training and in the three month period after the training for trained and untrained groups. Means and standard deviations will be provided by the services, that is, no individual data will be shared with researchers.

To meet the final objective, we will compare the IMD quintiles for attendees at the programmes in the three month period post-training with the IMD quintiles for the IRAS 336469

Derbyshire population. The expectation is that the % of people in socially deprived quintiles will be higher for the programmes than for the Derbyshire population.

SPSS and Excel spreadsheets will be used to store, organise and assist in analysis of the quantitative data from multiple sources.

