### **3.Plan of investigation**

#### **3.1 Design**

The objectives will be achieved through a mixed methods evaluation. This will consist of a process evaluation to assess acceptability, feasibility and use of the learnt techniques in practice (Moore *et al.*, 2015), and a concurrent pre-test post-test measurement of outcomes, or controlled pre-test post-test measurement of outcomes where possible (Aggarwal & Ranganathan, 2019; NICE, 2012).

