## DCHS NHS Pulmonary Rehabilitation Programme

We would expect the increase in the mean CRDQ score at 6 weeks in 2024 (post training) to be larger than the increase in the mean CRDQ score in 2023 (pre training). We are unlikely to have statistical power to detect small differences based on numbers of service users if we limit the 'post' time period to the three month study period in 2024 and the corresponding 'pre' time period in 2023. We need to extend this request for data to cover a six month period.

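### For pulmonary rehabilitation, section 3.10.5 sets three-month windows and trained/untrained groups, although section 3.9.3 calls for six months and this service has no untrained group; its data request also omits the SD of change

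*Combined protocol and SAP*

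**What the plan says.** Section 3.10.5 gives the only analysis rule for aggregate outcomes: "we will compare mean change in an outcome in a three month period before the training and in the three month period after the training". The sentence goes on to apply this to trained and untrained groups, and no service is singled out. It is followed by "Means and standard deviations will be provided by the services, that is, no individual data will be shared with researchers".

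Other sections treat pulmonary rehabilitation differently:

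- **Window.** The pulmonary rehabilitation part of section 3.9.3 contrasts the CRDQ gain in 2024 with that in 2023. On three-month periods it says "We are unlikely to have statistical power to detect small differences based on numbers of service users", and then "We need to extend this request for data to cover a six month period". Section 3.7 requests data from both services "for a three - six month period in 2024 when trained staff have delivered programmes", with a corresponding period in 2023.
- **Groups.** Section 3.1 promises pre-test post-test measurement, "or controlled pre-test post-test measurement of outcomes where possible". Section 3.2 explains that one weight management staff member takes a group through its sessions, so service users can be linked to trained or untrained staff, and adds "This is not possible for the pulmonary rehabilitation service where different staff work with different service users throughout the programme". Section 3.7 is consistent with this: "For the weight management service, a control group will consist of programmes run by non-trained staff". No control is defined for pulmonary rehabilitation.
- **Data items.** In section 3.7 the weight management list asks for the SD of weight loss. The pulmonary rehabilitation list asks for SDs of scores at baseline and six weeks, but for change in the CRDQ and in each secondary measure it asks only for the mean. The number of people with scores at both times is not listed.

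**The concern.** The CRDQ is this service's primary outcome, and the 2024 against 2023 comparison is its only outcome contrast that bears on the training. The section that should specify that comparison describes something else.

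Three things follow if section 3.10.5 is applied as written. The analysis uses the shorter window that section 3.9.3 considers insufficient for small differences, even if six months of data are obtained. It calls for an untrained group that does not exist here. And if the service supplies only what the itemised list requests, the standard error of a difference in mean change cannot be calculated, because SDs at two time points do not give the SD of change without the correlation between them. Individual records are not shared for this comparison, so the gap could not be filled later from the same source. The consenting participants' paired scores would be only a partial substitute: they cover 2024 alone, and section 3.8.1 restricts them to people with COPD.

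**Working it through.** **Inputs.** Section 3.9.2: 8-12 people per programme, 6 venues, two cohorts in three months. Section 3.9.3 (weight management): 80% power, 5% significance. Not in the documents and so assumed: constant intake over six months, equal numbers in 2023 and 2024, paired scores for every attender, no clustering. No CRDQ SD or target difference is given, so results are in units of the SD of change.

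**Reproducing the plan's figures.**
- Attenders: 6 × 8 × 2 = 96 and 6 × 12 × 2 = 144, as stated.
- Weight management sample size, two-sided: 2 × (1.960 + 0.842)² × 1.6² / 0.4² ≈ 251.2, rounded up to 252 per group, as stated. The same formula is used below.

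**Three against six months.** Detectable difference at 80% power = (1.960 + 0.842) × √(2/n), with n per period. The 95% CI half-width = 1.960 × √(2/n).

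| Window | n per period | Detectable difference | CI half-width |
|---|---|---|---|
| Three months | 96 | 0.404 | 0.283 |
| Three months | 144 | 0.330 | 0.231 |
| Six months | 192 | 0.286 | 0.200 |
| Six months | 288 | 0.233 | 0.163 |

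Doubling the window narrows the interval by 1 − 1/√2 = 29%. For an assumed effect of 0.25 SD of change, power is 41-56% at three months and 69-85% at six. If only 70% have paired scores (assumed), the detectable differences are 0.39-0.48 and 0.28-0.34.

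**SD of change.** With equal SDs at both times, SD of change = SD × √(2(1 − r)), where r is the baseline to six-week correlation. The plan gives no r. Illustrative values:
- r = 0.3: √1.4 = 1.18 × SD
- r = 0.5: √1.0 = 1.00 × SD
- r = 0.8: √0.4 = 0.63 × SD

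For a difference of 0.25 time-point SD, the number needed per period runs from 352 (r = 0.3) to 101 (r = 0.8), about a 3.5-fold range. The listed items therefore leave the precision undetermined.

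**Timetable.** Section 6 puts training in July-August 2024, the end of service-user outcome collection in February 2025, and analysis and reporting up to March 2025. It gives no training date for this service. Six months of starters, plus six weeks to the second assessment:
- trained by early July: starters July-December, last scores about 11 February 2025
- trained by end July: starters August-January, about 14 March 2025
- trained by end August: starters September-February, about 11 April 2025

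Only the first case stays within outcome collection. The other two also go beyond the 2024 period in section 3.7.

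**The case against.** The strongest reply is that the intent is clear. Section 3.9.3 is the only statement on the window specific to this service, and it names both six months and the 2024 against 2023 contrast. The three to six months in section 3.7 is compatible with that. Sections 3.2 and 3.7 confine the control to weight management, so no one could build an untrained pulmonary rehabilitation group. The promise of standard deviations in section 3.10.5 directly follows the sentence on mean change and may be meant to include the SD of change.

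Much of this stands. It shows that section 3.10.5 is a general sentence not brought into line with the rest of the plan, rather than a plan without a contrast. It does not remove the conflict: section 3.10.5 still analyses three months, and the itemised list omits for one service what it requests for the other.

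Some stronger readings are tempting but not supported:
- A reader might infer that section 3.10.5 uses a different comparison year because it says only that the first period precedes training. Section 3.9.3 itself labels 2023 as pre-training, so the two are consistent.
- A reader might infer that the window has been left open so that it can be chosen on the results. Nothing in the documents suggests this.
- A reader might infer that the plan treats the baseline-to-six-week gain as a training effect. Section 3.9.2 links that improvement to attending the programme, and section 3.10.4 claims no training effect. The lack of a caveat contradicts nothing.

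**Conclusion.** The point holds as an inconsistency between the analysis section and the rest of the plan, confined to the aggregate analysis for pulmonary rehabilitation. The window and the grouping in section 3.10.5 do not fit this service, and the itemised request may leave the main comparison without a valid standard error. Whether it does depends on how the general promise of standard deviations is read.

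The loss from using three months rather than six is a detectable difference of about 0.33-0.40 instead of 0.23-0.29 SD of change. Both ranges are optimistic, because they rest on constant intake, complete pairs and no clustering. Without a CRDQ SD or target difference, the documents do not show whether that loss matters clinically. The correction is cheap and should be made before the services extract data.

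**What to change.** 1. **Section 3.10.5.** Limit the trained/untrained wording to weight management. Add for pulmonary rehabilitation: the 2024-minus-2023 difference in mean CRDQ change with 95% CI, over the six-month window of section 3.9.3, using the same calendar months in each year, described as an uncontrolled historical comparison. State six months for this service in section 3.7 as well.
2. **Section 3.7.** For the CRDQ and each secondary measure, in both years, request the SD of change and the number with paired scores.
3. **If six months does not fit.** Once this service's training date is known, and before data are requested, fix one shorter window and state it identically in sections 3.7, 3.9.3 and 3.10.5 with its achieved precision. On the same assumptions, five months (160-240 per period) detects 0.26-0.31 SD of change and four months (128-192) detects 0.29-0.35.

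As a reporting suggestion only, section 3.10.4 could say that the baseline-to-six-week changes describe change after the programme and, with no untrained comparator, do not isolate the training.

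The cost is a few sentences and two extra columns in the request. The downside is time: unless staff are trained by early July 2024, six months of starters would run beyond 2024 and past the February 2025 end of outcome collection. Confounding by other changes between years remains whichever window is used.
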